8.5 Adverse Event Reporting

Toxicities (including suspected reactions) that meet the expedited reporting criteria as outlined in [Section 16.0](#) of the protocol must be reported to the Operations Office, Study Chair and NCI via CTEP-AERS, and to the IRB per local IRB requirements.

CLOSED EFFECTIVE 10/15/15

9.0 STUDY CALENDAR

	α		†		Π		∇		∑							
	Wk															
REQUIRED STUDIES																
	0	1	2	3	4	5	6	7	8	9	10	11	12	13	14	24
	D	D	D	D	D	D	D	D	D	D	D	D	D	D	D	D
PRE STUDY	1	8	15	22	29	36	43	50	57	64	71	78	85	92	99	169
PHYSICAL																
History *																
Physical Exam (Height, Weight and Performance Status)																
Toxicity Assessment			X				X						X			X
Drug Compliance (Intake calendar, pill count & AI adherence)			X				X						X			
Assessment of suicidality δ			X				X						X			X
LABORATORY																
FSH (if necessary)																
AST/ALT																
Total bilirubin																
Serum creatinine																
PATIENT COMPLETED QUESTIONNAIRES Σ																
S1202 BPI-SF													X			X
S1202 WOMAC		X	X										X			X
S1202 M-SACRAH		X	X										X			X
S1202 FACT-ES		X	X										X			X
S1202 Global Ratings of Change in Joint Pain and Stiffness			X										X			X
S1202 PHQ-9		X											X			

Calendar continued on next page.
Click here to see [footnotes](#).

	α		†		π		√		∫							
	Wk															
REQUIRED STUDIES	0	1	2	3	4	5	6	7	8	9	10	11	12	13	14	24
	D	D	D	D	D	D	D	D	D	D	D	D	D	D	D	D
PRE STUDY	1	8	15	22	29	36	43	50	57	64	71	78	85	92	99	169
STAFF ADMINISTERED FORMS																
S1202 Onstudy Form																
S1202 Treatment Form			X				X						X			
S1202 Supplemental Agents Reporting Form			X				X						X			X
S1202 Adverse Events Reporting Form (toxicity notation)			X				X						X			X
S1202 Cover Sheet for Patient Completed Questionnaires			X				X						X			X
S1202 Patient Treatment Satisfaction Form													X			
PROCEDURES																
Whole Blood for DNA #		X														
Blood for serum biomarkers #		X											X			
Telephone call to patient δ															X	
TREATMENT																
Dispense blinded study drug		X											X			
Duloxetine/Placebo 30mg (1 capsule) °		X											X			
Duloxetine/Placebo 60mg (2 capsules) °			X	X	X	X	X	X	X	X	X	X				

NOTE: Forms are found on the protocol abstract page on the SWOG website (www.swog.org). Forms submission guidelines may be found in [Section 14.0](#).

NOTE: Timing of the follow-up assessments are based on the start date of protocol treatment.

Click here to see [footnotes](#).

Footnotes

- α Patient reported questionnaires and blood draw must be completed prior to starting blinded drug.
- Ω On Day 15, review only the intake calendar and record AI adherence in the patient record. Do not perform pill count. See [Section 7.2b](#).
- δ Adverse events will be collected on the phone call. Report adverse events on the **S1202** Adverse Event Summary Form. Phone call must be completed within +/- 2 days from Day 99.
- ≠ [See Section 15.1](#).
- † Assessments must be completed during Day 15-21.
- ‡ Assessments must be completed during Day 40-46.
- √ Assessments must be completed during Day 79-85.
- ¥ Assessments must be completed within +/- 7 days from Day 169.
- β After the pill count, return enough pills to the patient to complete the Day 85-91 taper. See [Section 7.2b](#).
- Σ Administer questionnaires at the scheduled assessments even if the patient goes off protocol treatment prior to Day 85 for any reason. **S1202** Cover Sheet for Completed Questionnaires must be completed and included with the submission of patient questionnaires. See [Section 7.2](#) and [15.2](#).
- ο Patient is to take study drug daily. See [Section 7.1](#).
- * A statement that musculoskeletal symptoms started or worsened since initiation of adjuvant AI therapy must be documented in the patient's medical record at prestudy.
- ~ Must be performed within 28 days prior to registration.

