- Once study drug is received at the clinical trial site: The designated site coordinator verifies and matches the information on each of the 3 bottles and labeled resealable bag to the packing slip, signs off on the packing slip, and faxes completed form to Biologics to validate shipment has been received and is accurate.
- The site investigators are responsible to fill in the "Date Dispensed" on the label of the resealable bag and each of the study drug bottles prior to dispensing the study drugs to the patient.
- The site investigator should provide instructions to subjects on drug administration, missed dose, adherence, and drug return.

4. Drug Accountability

The investigator, or a responsible party designated by the investigator, must maintain a careful record of the receipt, disposition, and return of all drugs received using the Investigational Agent Accountability Record for Oral Agents (Oral DARF). The Oral DARF can be found on the NCI home page (<http://ctep.cancer.gov>). A separate Blinded Drug Accountability Record must be maintained for each patient ID number on this protocol. Electronic logs are allowed as long as a print version of the log process is the exact same appearance as the Oral DARF.

5. Drug Return and/or Disposition Instruction

- a. Drug Returns: All unused drug (unopened and unused vials remaining when a subject goes off treatment, and expired vials) should be destroyed on-site in accordance with institutional policy and documented accordingly on the DARF. Opened bottles with remaining tablets should be documented in the patient-specific accountability record (i.e., logged in as "# of capsules returned") and destroyed on-site in accordance with institutional policy.
- b. Drug Expiration: If packaging does not have expiration date, check with drug ordering designee and/or PI at site to confirm receipt of ongoing stability testing letter from Lilly when internal drug audits are performed.

6. Questions about drug orders, transfers, returns or accountability should be addressed to [name] at Biologics, Inc. ([name] or [contact]).

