7.1 Treatment

Agent	Dose	Schedule
Blinded drug (duloxetine 30 mg or placebo)	1 capsule PO Daily	Days 1-7
Blinded drug (duloxetine 30 mg or placebo)	2 capsules PO Daily	Days 8-84
Blinded drug (duloxetine 30 mg or placebo)	1 capsule PO Daily	Days 85-91

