7.2 Study Plan

a. Initial Visit

Before beginning the intervention, patients will have a general physical exam (including recording of weight and height) and a mandatory blood draw for whole blood and serum (see [Section 15.1](#)). The patient will complete the **S1202** Brief Pain Inventory–Short Form (BPI-SF) prior to registration to confirm eligibility (see [Section 5.2d](#)). Patients will complete the following questionnaires prior to beginning treatment with blinded study drug:

S1202 Western Ontario and McMaster Universities Osteoarthritis (WOMAC) Index (Version 3.1)

S1202 Modified-Score for the Assessment and Quantification of Chronic Rheumatoid Affections of the Hands (M-SACRAH)

S1202 FACT – ES Trial Outcome Index (Version 4)

S1202 Patient Health Questionnaire-9 (PHQ-9)

It should take the patient about 20-25 minutes to complete the questionnaires. See [Section 15.2](#) for instructions for administration of the questionnaires.

The nurse or CRA must complete the **S1202** Cover Sheet for Patient-Completed Questionnaires.

Bottle #1 and #2 are dispensed at this visit. Patients will take 1 capsule daily for the first 7 days, then increase the dose to 2 capsules daily. The dose that should be taken each day should be listed on the patient calendar (see [Section 15.2c.1](#)).

b. Follow-up Visits

Follow-up visits will occur on Day 15, 43, 85, and 169 after start of treatment. Drug adherence will be ascertained by the nurse or CRA by review of the patient completed **S1202** Intake Calendar on Day 15, 43, and 85, as well as count of blinded drug capsules on the Day 43 and 85 visits. After the Day 85 pill count, the nurse or CRA must dispense bottle #3 to the patient to complete the Day 85 to Day 91 taper. Counts of blinded drug capsules remaining should be recorded on the **S1202** Treatment Form and the patient's medical record through the Day 85 visit. Adherence to AI should be recorded on the **S1202** Treatment Form at every visit. Adverse events will be assessed and recorded on the **S1202** Adverse Event Summary Form through the Day 85 visit. Use of pain medications, steroids, physical therapy, and acupuncture will be recorded on the **S1202** Supplemental Agents Reporting Form.

The nurse or CRA will contact the patient by telephone on Day 99 to assess adverse events following study drug discontinuation. Adverse events will be recorded on the **S1202** Adverse Event Summary Form

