Patients will be instructed to complete the following questionnaires at the Day 15, 43, 85, and 169 visits. It takes about 20-25 minutes to complete the questionnaires.

S1202 Brief Pain Inventory Short Form (BPI-SF)

S1202 Western Ontario and McMaster Universities Osteoarthritis (WOMAC) Index (Version 3.1)

S1202 Modified-Score for the Assessment and Quantification of Chronic Rheumatoid Affections of the Hands (M-SACRAH)

S1202 FACT – ES Trial Outcome Index (Version 4)

S1202 Global Ratings of Change in Joint Pain and Stiffness

Patients will also be instructed to complete the following self-administered questionnaire at the Day 43 and 85 visits. It takes about 5-10 minutes to complete the assessment.

S1202 Patient Health Questionnaire-9 (PHQ-9).

The nurse or CRA will also complete the **S1202** Cover Sheet for Patient-Completed Questionnaires at each visit to indicate whether or not the patient completed the questionnaires, if the patient required assistance and the method for completing the questionnaires. If one or more of the questionnaires was not completed, an overall reason must be indicated on the Cover Sheet. See [Section 15.2](#) for detailed instructions for administration of the questionnaires.

Additionally, at the Day 85 visit, blood will be drawn for serum biomarkers (see [Section 15.1](#)).

All patients must taper off study drug after the Day 85 visit by decreasing the dose to 1 capsule daily for 7 days. After completing the taper of the study drug, if a patient wishes to take commercially-available duloxetine, she should take at least 7 days of duloxetine 30 mg daily prior to increasing the dose to 60 mg daily, in order to minimize the chance of developing side effects. She is permitted to start this at any time following completion of the taper of the study drug (Day 92).

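### Calendar footnote β and Section 7.2b name different sources for the Day 85-91 taper capsules, footnote β fails on the protocol's own capsule counts, and the taper's start is ambiguous when the visit falls before Day 85

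*Combined protocol and SAP*

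**What the plan says.** **Source of the taper capsules.** Footnote β of Section 9.0 reads "After the pill count, return enough pills to the patient to complete the Day 85-91 taper" and refers the reader to Section 7.2b. Section 7.2b says that, once the Day 85 count is done, "the nurse or CRA must dispense bottle #3 to the patient to complete the Day 85 to Day 91 taper". At the initial visit, "Bottle #1 and #2 are dispensed at this visit", so bottle #3 is still at the site. In the calendar, the row for dispensing blinded drug also carries a mark at Week 12.

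**Supply.** Section 3.1f gives 7 capsules each in bottles 1 and 3, and 154 in bottle 2.

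**Schedule.** Section 7.1 sets one capsule daily on Days 1-7, "2 capsules PO Daily" on Days 8-84, and one capsule daily on Days 85-91.

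**Start of the taper.** Section 7.1, the bottle #3 sentence in Section 7.2b and footnote β all give Days 85-91. The last paragraph of Section 7.2b is worded differently: "All patients must taper off study drug after the Day 85 visit by decreasing the dose to 1 capsule daily for 7 days". Footnote √ of the calendar says of that visit: "Assessments must be completed during Day 79-85".

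**The concern.** A site working from the calendar and a site working from Section 7.2b would take the taper capsules from different places. The calendar version presupposes capsules left over in the counted bottle, so it matters whether the supply provides any.

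The visit window raises a second question. The visit called Day 85 may be held up to six days earlier. A taper tied to the visit and a taper tied to Days 85-91 then begin on different dates, and the visit instructions do not say what becomes of the capsules still in bottle #2. At stake is whether all patients receive the same duration at two capsules and the same taper.

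**Working it through.** **Inputs.** Schedule from Section 7.1; bottle contents from Section 3.1f; visit window from footnote √. Full adherence is assumed: no missed doses and no dose reduction.

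**Step 1: reproduce the supply.**
- Days 1-7: 7 × 1 = 7 (bottle 1).
- Days 8-84: (84 − 8 + 1) × 2 = 77 × 2 = 154 (bottle 2).
- Days 85-91: 7 × 1 = 7 (bottle 3).
- Total: 7 + 154 + 7 = 168.

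The three bottles match Section 7.1 exactly. Bottle 2 has no overage, and bottle 3 is the size of the taper.

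**Step 2: what the pill count finds.** On visit day v, before that day's dose, bottle 2 holds 154 − 2 × (v − 8). Section 7.1 still needs 2 × (85 − v) from that bottle to reach the end of Day 84.

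| Visit day | Left in bottle 2 | Needed through Day 84 | Spare | At least 7 left for footnote β? | Two-capsule days lost if the taper starts the next day |
|---|---|---|---|---|---|
| 79 | 12 | 12 | 0 | yes | 5 |
| 80 | 10 | 10 | 0 | yes | 4 |
| 81 | 8 | 8 | 0 | yes | 3 |
| 82 | 6 | 6 | 0 | no | 2 |
| 83 | 4 | 4 | 0 | no | 1 |
| 84 | 2 | 2 | 0 | no | 0 |
| 85 | 0 | 0 | 0 | no | 0 |

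On Days 82-85 the counted bottle cannot supply a 7-capsule taper. On Days 79-81 it can, but only with capsules that Section 7.1 assigns to the days through Day 84. The spare column is zero throughout, so footnote β cannot be followed together with Section 7.1 on any day of the window.

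On Day 85 itself, footnote β works only for a patient who has missed doses or had a dose reduction. Each fully missed two-capsule day leaves 2 capsules, so at least 4 such days are needed (4 × 2 = 8, which covers 7).

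**Step 3: start of the taper.** If the Section 7.2b paragraph is read literally and the taper starts the day after the visit, the two-capsule days lost are 84 − v for a visit on Days 79-84. This gives the last column: 5 days at most, none on Day 84. Under the Days 85-91 wording the loss is zero for every visit day.

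**Step 4: is there a reading that fits?** Suppose the patient keeps the bottle 2 remainder and also receives bottle 3. On Day 79 she then has 12 + 7 = 19 capsules, and Section 7.1 requires 12 + 7 = 19. The same equality holds on every day through Day 85. The supply is therefore adequate. The missing element is an instruction saying how it is to be used at an early visit.

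**The case against.** The strongest reply is that this is a leftover footnote. Footnote β sends the reader to Section 7.2b, which names bottle #3, and the supply is built around that bottle. The calendar as extracted does not show where β attaches. The start of the taper is also better settled than one paragraph suggests: Section 7.1, the bottle #3 sentence and footnote β all say Days 85-91. The very paragraph that ties the taper to the visit also places its completion at Day 92, and Section 7.4d sets 13 weeks (91 days) of treatment. Much of this stands. The visit-based wording is an ambiguity created by the Day 79-85 window, not a second stated start date. Even so, footnote β is operative text that conflicts with the section it cites.

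Several stronger readings are tempting, and the documents do not support them:

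- **A patient seen on Days 79-84 cannot follow Section 7.1, because she needs 19 capsules and receives 7.** This requires the site to take bottle #2 away. No text orders that for a patient still on treatment. Section 7.2b also requires a count on Day 43, after which the same bottle must last through Day 84. The line in Section 3.1f.5, "Opened bottles with remaining tablets should be documented in the patient-specific accountability record", stands under drug returns, where the preceding sentence concerns patients going off treatment.
- **Sites following both texts would give a double supply.** A fully adherent patient has no spare capsules on any day of the window.
- **A late visit leaves a gap in dosing.** Bottle #2 does run out after Day 84, but a visit after Day 85 is already outside the calendar window. Section 15.2b.5, on missed appointments, governs questionnaires and not drug supply.
- **The Day 99 call should be re-timed.** The calendar fixes the call at Day 99 within 2 days. Moving it would be a new clinical rule, not a reconciliation of text.

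**Conclusion.** The point holds in a limited form. Two current instructions name different sources for the taper capsules, and one of them fails on the protocol's own counts for a fully adherent patient on every day from 79 to 85. Separately, the visit-based taper wording leaves room for a loss of up to 5 days at two capsules. That figure assumes a Day 79 visit, that day's dose taken in full, and a taper starting the next day. It is the limit of a literal reading and not an expected loss.

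The effect on the primary endpoint is likely small. Week 12 questionnaires completed inside the calendar window come at or before the start of the taper. The case for a correction rests on consistent dosing and taper across sites, and no change in power or bias is claimed.

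**What to change.** The sponsor should reconcile Section 7.1, both taper statements in Section 7.2b, and footnotes β and √ of Section 9.0, so that together they:

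1. name one source of the taper capsules;
2. give one start of the taper, whether a fixed day or the visit;
3. say what happens to the bottle #2 remainder when the visit falls on Days 79-84.

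Which rule applies is the sponsor's decision; this review takes no position on it. The cost is a short wording amendment and a matching site dispensing instruction. Bottle #3 is already part of the initial shipment under Section 3.1f. If capsules are handed back at an early visit, the recorded pill count must allow for them.

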10.0 CRITERIA FOR EVALUATION AND ENDPOINT DEFINITIONS

10.1 Primary Outcome

Reduction in average joint pain according to the Brief Pain Inventory – Short Form (BPI-SF) average pain score (item #4). This item has a scale of 0 to 10 with 0 indicating “No pain” and 10 indicating “Pain as bad as you can imagine” (assessed at Weeks 2, 6 and 12).

10.2 Main Secondary Outcome

Reduction in worst joint pain according to the BPI-SF worst pain score (item #2) at 12 weeks. This item has a scale of 0 to 10 with 0 indicating “No pain” and 10 indicating “Pain as bad as you can imagine”.

10.3 Performance Status

Participants will be graded according to the Zubrod performance status scale.

POINT	DESCRIPTION
0	Fully active, able to carry on all pre-disease performance without restriction.
1	Restricted in physically strenuous activity but ambulatory and able to carry out work of a light or sedentary nature, e.g., light housework, office work.
2	Ambulatory and capable of self-care but unable to carry out any work activities; up and about more than 50% of waking hours.
3	Capable of limited self-care, confined to bed or chair more than 50% of waking hours.
4	Completely disabled; cannot carry on any self-care; totally confined to bed or chair.

11.0 STATISTICAL CONSIDERATIONS

11.1 Primary Objective

Joint pain will be assessed using “average pain” according to the BPI-SF. Enrollees must currently be taking AIs and must exhibit joint pain with a minimum BPI-SF average pain score of 4; scores of 4 to 10 are considered to reflect moderate to severe pain. (42) Patients will be stratified at randomization by the use of average baseline pain according to the BPI (4-6 vs 7-10) and prior taxane use (yes vs. no). The primary assessment time of 12 weeks, upon which power calculations are based, corresponds to completion of the intervention and allows cross-trial comparisons to be made with **S0927**, which is evaluating a different pharmacologic agent for treatment of AIMSS in the same patient population.

This study stipulates an $\alpha=0.05$ two-sided test, with an estimated 5% non-adherence (reducing the nominal effect size) and 15% dropout rate (increasing the total required sample size) at 12 weeks after randomization. (16, 43) In addition, the design will

incorporate a 10% contamination rate (which also reduces the nominal effect size) based on the assumption that a portion of the patients will not benefit from intervention based on joint pain with a different etiology that is not associated with AI treatment (this has a similar impact on power calculations as a “drop-in” rate).[\(44\)](#)

The proposed sample size incorporates adjustments for loss, non-adherence, and contamination. The power for the design will be a function of the difference detected and the standard deviation at 12 weeks after randomization.

Difference Detected: Although a difference of 2 points in the BPI has been identified as representing a clinically meaningful *individual* level difference, for power calculations assessing group-level differences, we will test a smaller effect. [\(45\)](#) Specifically, an incremental difference in pain reduction due to duloxetine over placebo of about 1.0 points at 12 weeks has been repeatedly found in the setting of fibromyalgia. [\(43,46\)](#)

Standard Deviation: Multiple studies of AI-induced joint pain have found the standard deviation for BPI “average pain” at follow-up on placebo to be about 2.0 to 2.5 points. [\(47,8\)](#) The design assumes a common standard deviation between arms; a similar standard deviation has been observed in a pilot study of duloxetine. [\(16\)](#) We assume a SD of 2.3 points at 12 weeks for this study (the estimated average SD found in Arnold, Clin J Pain, 2009). [\(8\)](#)

For a 1.0 point difference and a 2.3 point SD at 12 weeks, with other parameters as specified above, 270 eligible patients would be required for 80% power under a two-arm normal design. Power will be higher with lower observed standard deviation or a larger observed difference.

The following considerations clarify the impacts of loss, non-adherence, and contamination on the sample size calculations:

- A two-arm normal design with $\alpha=0.05$ two-sided test and a 2.3 point SD to detect a difference of 1.0 points requires approximately 166 patients (83 per arm) for 80% power.
- An estimated 5% non-adherence and 10% contamination both reduce the nominal effect size, from 1.0 points to 0.85 points. This increases the required sample size to 230 total patients (115 per arm).
- To account for an estimated 15% dropout rate, the total required sample size must be further increased by 15%, as in $230/0.85 = 270$ total patients.

The primary analysis will rely on longitudinal measures of BPI at Weeks 2, 6, and 12 for improved power. (Thus the proportion of patients with zero follow-up observations will likely be less than the specified 5% non-adherence and 15% dropout at 12 weeks used for power calculations.) Assessment windows of +/- 7 days, +/- 14 days, and +/- 14 days will be allowed for the 2, 6, and 12 week timepoints. (Given the primary analysis is based on longitudinal measures, a sensitivity analysis will consider all observations within 14 weeks of registration.) The analysis will be performed using mixed models, adjusted for baseline average pain and the stratification factors. To minimize missed assessments, SWOG utilizes an electronic system to remind institutions in real-time that patients are due for follow-up assessment. If the proportion of missing follow-up data is >20% (the sum of the specified targets for non-adherence and dropout), plots of mean pain levels over time for patients grouped by number of follow-up responses will be examined to check for patterns of informative missing data. Should these plots suggest that data may not be missing at random, pattern mixture models, which models missingness patterns through stratification, will be utilized for analysis of the longitudinal BPI pain data. [\(48, 49\)](#)

Under the intention-to-treat principle, the primary analysis will be based on all eligible, randomized patients. To allow for an ineligibility rate of 8%, as found on our recent Symptom Control study [S0715](#), a total of 294 patients will be enrolled to achieve 270 eligible patients.

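### Section 11.1 uses plots that can only contradict missing completely at random, and that are not specified by arm, to decide that data are not missing at random and to choose the model for the primary endpoint.

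*Combined protocol and SAP*

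**What the plan says.** Section 11.1 makes a mixed model of BPI average pain at Weeks 2, 6 and 12 the primary analysis, adjusted for baseline pain and the stratification factors. A check on missingness follows, but only if missing follow-up data exceed 20%, a figure explained as the 5% non-adherence target plus the 15% dropout target. In that case "plots of mean pain levels over time for patients grouped by number of follow-up responses will be examined". The consequence comes next: "Should these plots suggest that data may not be missing at random, pattern mixture models", which stratify on the pattern of missingness, are to be used for the longitudinal pain data.

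The section does not say:
- whether the plots are made by treatment arm;
- what separation of the curves counts as a signal;
- which identifying restriction the pattern mixture model would use;
- whether the mixed-model result would still be reported as primary;
- whether the 20% refers to Week 12 or to all visits.

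The only other sensitivity analysis in 11.1 widens the set of observations by timing (those within 14 weeks of registration) and does not address missingness.

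**The concern.** Equal curves across response groups are what missing completely at random (MCAR) implies. MAR implies no such thing. If patients stop answering because of pain they have already reported, data are MAR and the curves separate, yet a correctly specified likelihood mixed model remains valid. Separated curves therefore do not support the conclusion the section draws from them.

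The reverse error is also possible. The arm comparison is biased when informative loss differs between arms. If the plots combine the arms, high-pain losses in one arm can offset low-pain losses in the other, and the curves then look alike.

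At stake is the choice of model for the primary endpoint, made after the data are seen, on a signal that does not measure the stated condition. No MNAR analysis is planned outside this route.

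**Working it through.** **1. Design inputs (Section 11.1).** The plan states "We assume a SD of 2.3 points at 12 weeks for this study". Non-adherence and contamination "both reduce the nominal effect size, from 1.0 points to 0.85 points". Per arm, n = 2(1.960 + 0.842)² × SD² / difference².
- Difference 1.0: 2 × 7.849 × 5.29 = 83.04 per arm. The plan has 83 per arm, 166 in total (168 if rounded up).
- Difference 0.85: 83.04 / 0.7225 = 114.9, so 115 per arm and 230 in total, as stated.
- Dropout: 230 / 0.85 = 270.6. The plan has 270.
- Ineligibility: 270 / 0.92 = 293.5, so 294, as stated.

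The design figures reproduce. The SD of 2.3, the effect of 0.85 and the 270 patients are used below.

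**2. What the plots can show.** MAR means that the chance of a missing score depends only on observed scores. If dropout before Week 6 rises with the Week 2 score, patients with one response have a higher Week 2 mean than completers. This separation arises under MAR. MNAR dropout can produce the same picture, because the current score correlates with earlier ones. Observed means by response count therefore cannot tell the two apart.

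**3. First illustration.** 3,000 trials per scenario, 135 patients per arm, SD 2.3, constant effect 0.85. Assumptions not in the documents: visit correlation 0.6; a Week 2 score for everyone; monotone dropout with hazard expit(−2 + slope × x). Under MAR, x is the last observed pain in SD units. Under MNAR, x is the current residual, with opposite sign in the two arms. The visual reading is replaced by tests of group differences at Weeks 2 and 6, total alpha 0.05, arms combined.

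| Dropout | Slope | Check fires | Mean Week 12 estimate |
|---|---|---|---|
| MCAR | none | 4% | not tabulated |
| MAR | 0.4 / 0.6 / 0.8 | 64% / 94% / 99.6% | 0.85 / 0.85 / 0.85 |
| MNAR, opposite by arm | 0.4 / 0.6 / 0.8 | 6% / 7% / 7% | 0.67 / 0.57 / 0.46 |

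Drawn by arm, the check fires in 19%, 43% and 68% of the opposite-direction trials, but still in 42% to 97% under MAR.

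**4. Second illustration.** 1,500 trials of 270 patients under other assumptions: baseline SD 1.3; correlation 0.6; effects 0.6, 0.85 and 0.85 at Weeks 2, 6 and 12; dropout slope 0.5 per point; 25% missing over all visits (35% to 36% at Week 12). A gap counts as visible if the Week 2 difference between completers and patients with one or two responses has |z| > 1.96.

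| Dropout | Gap, arms combined | Visible | Benefit lost at Week 12 (of 0.85) |
|---|---|---|---|
| MCAR | 0.01 | 5% | 0.00 |
| MAR | 1.91 | 100% | 0.00 |
| MNAR, same direction | 1.28 | 96% | 0.08 |
| MNAR, placebo only | 0.66 | 48% | 0.32 |
| MNAR, opposite by arm | −0.01 | 5% | 0.58 |

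The combined gap is roughly the average of the arm gaps. For opposite directions, (1.28 − 1.28)/2 = 0.00; for placebo only, (1.25 + 0.01)/2 = 0.63. Split by arm, the opposite-direction gaps are visible in 81% and 82% of trials and the placebo-only gap in 79%. Under MAR the by-arm gaps are still visible in 97% to 98%.

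**5. The 20% gate.** In step 3, missingness reaches at most about 14% at Week 6 and 26% at Week 12. Over all visits that is (0 + 14 + 26)/3 = 13%, and the gate opens in 0% of trials; it opens only if read as Week 12 missingness. In step 4, 25% over all visits opens it in 98% to 99% of trials on the all-visit reading. At 15% over all visits (21% to 22% at Week 12) it opens in about 1% or fewer on that reading. The three MNAR losses are then 0.03, 0.21 and 0.37, with no check run.

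**6. Cost of a wrong switch under MAR.** The plan does not define its pattern mixture model. Simple pattern-stratified versions gave estimates between 0.76 and 0.88 against a true 0.85, depending on how patterns were weighted: at most 0.85 − 0.76 = 0.09 points.

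**The case against.** The strongest reply has five parts.

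- **Arm.** Section 11.1 does not say that arms are combined. A reader might infer pooling from the grouping by response count, but the text is silent and the plots could be made by arm. This stands: the defect is that arm is not specified. Drawing by arm would not repair the inference, since by-arm curves still separate under MAR.
- **Missed dropout.** A reader might infer that the plots stay silent whenever dropout differs by arm. They do not. Combined plots showed one-arm MNAR dropout in about half of the trials in step 4, and same-direction dropout, where bias was small, in 96%. Full cancellation needs opposite directions of similar strength.
- **Plausibility.** Sections 7.4, 9.0, 14.4i and 15.2 keep questionnaires going after study drug stops, so stopping drug is not itself missing data. In the pilot (Section 2.0), 7 of 34 patients (20.6%) stopped for adverse events, most within days, so the assumed loss after Week 2 is not drawn from the documents. This limits how likely the bad case is. It does not exclude it.
- **Gate and proxy.** The check may never run, and a significance test is not a visual judgement. Both stand, so the firing rates describe the proxy.
- **Harm.** The wrong switch under MAR moved the estimate only modestly in the simple versions tried. This also stands, although the actual shift is unknown because no identifying restriction is stated.

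None of these makes the inference from separated curves to not missing at random valid when the check is used.

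**Conclusion.** The point holds as a fault in the decision rule. Differences between response groups are evidence against MCAR and cannot separate MAR from MNAR, so the rule can replace a valid mixed model. With arm unspecified, the plots can also miss informative dropout that differs between arms: fully when directions are opposite, partly when one arm is affected. Section 11.1 offers no other MNAR safeguard.

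In the illustrations, the Week 12 benefit under opposite-direction MNAR dropout fell short by 0.18 to 0.39 points (step 3) and by 0.58 (step 4), against a design effect of 0.85. These sizes depend on the assumed correlation, the dropout slopes, the proxy for visual reading and, in step 3, a Week 12 reading of the gate. They show the mechanism and do not forecast this trial. A reader might infer that the trial would usually abandon a sound primary analysis. The documents do not support that, because the switch needs the gate to open and a judgement for which no criterion is set. The sample size is unaffected.

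**What to change.** In Section 11.1:
1. Draw the plots by arm and response pattern, as description only.
2. Delete the inference that separated curves mean data are not MAR.
3. Keep the mixed model as the primary analysis whatever the plots show.
4. Pre-specify an MNAR sensitivity analysis with arm-specific shifts, run whatever the plots show. One option is multiple imputation of missing Week 12 BPI average pain under MAR, then shifting imputed values separately in each arm over a stated grid (for example 0 to 2 points, including opposite shifts), and reporting the shift at which the conclusion changes. A pattern mixture model with stated identifying restrictions is an alternative.

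The cost is a few sentences and some extra programming on data already collected. The primary result would then be reported with a sensitivity range alongside it.
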